#### **Sexual Encounter Profile (SEP): Questions 2 and 3**

The two questions from the Sexual Encounter Profile (SEP) deal with the ability to achieve vaginal penetration (SEP2), and the ability to maintain an erection long enough for successful intercourse (SEP3) will be analyzed as part of this study. This questionnaire will be completed at V2-V7 (week 0-24).

Chi-square analysis will be performed to compare the responses at each post dose visit with baseline response for the two treatment groups, namely, *hMaxi-K* (16,000 µg) and placebo. In addition, repeated measures logistic regression will be performed to analyze the effect of treatment groups and time points on the response to the SEP questions. The baseline and post baseline score for each SEP question will be a patient's percentage of "yes" responses to that question during the baseline and post baseline period, respectively.

ANCOVA will be used to analyze the mean change in SEP response from baseline to post baseline visits between *hMaxi-K* (16,000 µg) and placebo.

The above analysis will be repeated for comparison between the two treatment cohorts and between *hMaxi-K* 8000µg and placebo treatment groups.

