4.1 Inclusion Criteria

Eligible participants must meet the following inclusion criteria:

- a) Signed Informed Consent
- b) Be adult males over 18 years of age diagnosed with erectile dysfunction and whose ED is attributable to an underlying, stable medical condition such as hypertension and

atherosclerosis, antihypertensive medication, type I and type II diabetes mellitus, pelvic surgery and pelvic radiation, cerebrovascular accidents (stroke), multiple sclerosis, and Parkinson's disease;

- c) Participants must have been unable to have successful sexual intercourse for 3 months prior to study entry without specific ED therapy such as Vacuum Erection device (VED), Viagra™ (sildenafil), Cialis™ (tadalafil), Muse™ (alprostadiol), or intracavernous injection therapy with an erectile function domain score of IIEF >10 and < 21 at screening and baseline;
- d) Have been unable to tolerate, do not wish to continue, or have had unsuccessful results with, prior therapy for ED, e.g., Viagra™, intracavernous injection therapy, Muse™, or VED;
- e) If diabetic, documentation of HgA_{1c} less than or equal to 8.5 % prior to enrollment;
- f) If receiving medication for hypertension, documentation of blood pressure has been stable on the same medication for at least 2 months prior to enrollment;
- g) Be heterosexual and in a stable, monogamous relationship of at least six months duration;
- h) Agree to attempt intercourse with their partner at least four times per month while participating in the study;
- i) Agree not to use other treatments for ED while participating in this study;
- k) Have screening laboratory values and ECG that are within the normal range. See exclusion criterion below.
- l) Have a normal physical examination of the penis;
- m) If participant had a radical prostatectomy a PSA <0.4 for at least one year documented by 2 measurements during the preceding year;
- n) Be literate, able to give written informed consent, and comply with all study procedures and requirements.

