##### Primary objective

The primary objective of this study is to evaluate the potential efficacy and safety of a single intracavernous injection of *h*Maxi-K (16,000 µg) compared to placebo in males with erectile dysfunction longer than six months that was attributable to an underlying, stable medical condition upon penile rigidity or erection in males with erectile dysfunction longer than six months that is attributable to underlying, stable medical condition.

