## 6. Definition

- **Age:** The age will be calculated as the exact number of days between the date of birth and date of informed consent converted to years (i.e. difference in days/365.25). Age is the integer part of this value.
- **Baseline:** The time point at which randomization is performed will be the baseline time point. The last instance of data collected before administration of treatment will be considered as the baseline information for the respective parameter. If a patient has repeated assessments prior to the start of double-blind study drug, then the results from the final assessment made prior to the start of double-blind study drug will be used as baseline.
- **Body Mass Index (BMI):** BMI is obtained by dividing the weight (kg) by the square of height (m) i.e. weight (kg)/ height (m).
- **Change between baseline and post dose visits** for the parameters will be considered as the difference between the post baseline value and the baseline value (post baseline value – baseline value). This will be applicable to laboratory data and safety parameters.
- **Prior/ Concomitant Medication/Therapy:** All medications/therapies with end date prior to the date of treatment will be considered as prior medications. Concomitant medication will be defined as any medication taken between the day of dosing with study drug and the end of the 6 month study follow-up period (or final visit). Any medications started after the final visit will not be considered concomitant medications.
- **Treatment Emergent Adverse Events (TEAEs):** A treatment emergent adverse event (TEAE) will be considered as an event that is temporally associated with the use of the study drug, whether or not considered related to the study drug. All adverse events with start date on or after the date of treatment will be considered as TEAEs.

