#### **Efficacy endpoints**

The International Index of Erectile Function (IIEF) is a validated, self-administered questionnaire that has been shown to be a cross-culturally and psychometrically valid measure of male erectile dysfunction.

The test contains 15 questions in five domains:

- a) erectile duration/function (six items)
- b) orgasmic function (two items)
- c) sexual desire (two items)
- d) intercourse satisfaction (three items)
- e) overall sexual satisfaction (two items)

The summary tables against the data collected through the IIEF will include the descriptive statistics against the total and domain specific score by visit. The domain specific scores will be the sum of the scores against questions under the respective domain. The total score will be the sum of scores of all the questions. The listings will also be presented against all the data that is collected.

SEP is a diary in which subjects record each sexual attempt made throughout the study and is composed of 5 questions assessing sexual function. SEP 2 evaluates the penetrability of the erection and SEP 3 the maintenance of the erection.

The summary tables against SEP will include the number and percentages of subjects reporting yes/no against each of the questions. Corresponding listing will also be presented.

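### SAP 9.3 makes none of its three SEP2/SEP3 analyses decisive, and the first, a within-arm chi-square of unstated form and unit, cannot answer 16,000 µg versus placebo

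*SAP*

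**What the plan says.** SAP Section 9.3 lists SEP Questions 2 and 3 as primary outcome measures beside the IIEF erectile function domain. It plans three SEP analyses for 16,000 µg and placebo, then repeats them for pooled active versus placebo and 8,000 µg versus placebo:

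1. "Chi-square analysis will be performed to compare the responses at each post dose visit with baseline response for the two treatment groups".
2. A repeated measures logistic regression on treatment group and time point.
3. "ANCOVA will be used to analyze the mean change in SEP response from baseline to post baseline visits between" 16,000 µg and placebo.

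None is called decisive. The SAP's objective is a between-arm one: "The primary objective of this study is to evaluate the potential efficacy and safety of a single intracavernous injection of" hMaxi-K at 16,000 µg compared to placebo (SAP Section 4). SAP Section 9 makes efficacy tests one-tailed.

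Three units are in play. The diary is filled in per attempt (Protocol Appendix C). The summary tables count men: "The summary tables against SEP will include the number and percentages of subjects reporting yes/no against each of the questions" (SAP Section 9.2). The score in Section 9.3 is each man's percentage of yes "responses to that question during the baseline and post baseline period, respectively".

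On baseline, SAP Section 6 has a general rule: "The last instance of data collected before administration of treatment will be considered as the baseline information for the respective parameter". Section 9.3 uses a baseline period with no dates. The protocol synopsis places SEP at screening/baseline as well as at Visit 2. Protocol Sections 6.2 and 7.1, Protocol Appendix B and the SAP schedule show no SEP entry before Visit 2.

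**The concern.** Two statisticians following Section 9.3 could reach different verdicts on a primary measure. They could choose different forms of chi-square, different units, or a different one of the three analyses to lead with. An ordinary chi-square ignores the pairing of answers from the same man and has no direction.

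The more serious matter is what a within-arm test can show. A before-after gain in the 16,000 µg arm mixes any drug effect with placebo response, regression to the mean and the effect of being in a trial. With no decisive analysis named, such a gain could be reported as a positive primary result beside a between-arm comparison that shows nothing. For 16,000 µg and placebo alone there are 2 questions × 5 post-dose visits × 2 arms = 20 of these within-arm tests.

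**Working it through.** **The plan's own figure.** There is none for SEP. The only power calculation (Protocol 10.3.2, SAP Section 8) is for a mean score: difference 10.0 − 6.6 = 3.4, SD 2.5, alpha 0.0167. A one-sided two-sample t-test gives 81.0% power for 11 v 11 and 84.6% for 11 v 13, so the stated sample size reproduces. It says nothing about SEP.

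**Inputs.** From the documents: 11 men on 16,000 µg, 13 on placebo, one-sided 5%. Assumed: SEP3 baseline 5%, because criterion (c) implies a rate near zero ("Participants must have been unable to have successful sexual intercourse for 3 months prior to study entry without specific ED therapy"); SEP2 baseline 30–50%; and the within-man correlations given below.

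**Step 1: the two readings, one answer per man.** Let x1 and x2 be the numbers answering yes at baseline and post dose, c the men changing from no to yes, and b those changing from yes to no.
- Pearson: z = [(x2 − x1)/n] ÷ √[p̄(1 − p̄)·2/n], with p̄ = (x1 + x2)/(2n).
- McNemar: z = (c − b)/√(b + c).
- Example, 0 of 11 then 4 of 11: Pearson χ² = 4.89, p = 0.027. McNemar χ² = 4²/4 = 4.0, p = 0.046. Exact McNemar p = 2 × 0.5⁴ = 0.125 (all two-sided).

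**Step 2: size with no change.** Exact multinomial enumeration, n = 11 and 13, correlation 0.3–0.7, reject if z > 1.645.

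| | Pearson | McNemar |
|---|---|---|
| SEP3 (5%) | 0.03–0.5% | 0.04–0.6% |
| SEP2 (30–50%) | 0.2–3.6% | 1.6–5.4% |

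**Step 3: disagreement under a true 30-point rise, 11 men.**
- SEP3, 5% to 35%, correlation 0.1–0.3: Pearson and McNemar give different verdicts in 8–11% of trials.
- SEP2, 40% to 70%, correlation 0.1–0.5: 15–24%.

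**Step 4: equal 20-point rise in both arms, no drug effect.**
- SEP3 5% to 25% and SEP2 40% to 60%, one answer per man, 11 men, same correlations as in Step 3. By Pearson or McNemar, the 16,000 µg arm is significant against baseline in about 21–38% of trials.
- ANCOVA of change in each man's percentage, adjusted for baseline percentage, 11 v 13 men. It was simulated with 2 baseline attempts and 4, 11 or 22 post-dose attempts, and rejects in about 5–6%, close to nominal.

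**Step 5: the baseline window.** Criterion (h) sets a minimum rate of attempts: "Agree to attempt intercourse with their partner at least four times per month while participating in the study". Over 14 days that is 4 × 14/30.4 = 1.84 attempts per man. If attempts are Poisson, the share of men with none before dosing is:
- 14 days: exp(−1.84) = 16%
- 21 days: exp(−2.76) = 6%
- 28 days: exp(−3.68) = 2.5%

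**The case against.** Much can be said for the plan.

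- **A reader might infer that the SAP prescribes an unpaired, invalid test.** It does not. McNemar is also a chi-square test; the text leaves the form open.
- **A reader might infer inflated false positives.** With one answer per man, the unit of the SAP's own summary tables, Pearson is conservative. Simulation shows a clear excess (7.2–9.3% for SEP2) only if attempts are pooled, rates are moderate and each man's rate varies strongly between periods. No passage says attempts are pooled.
- **Disagreement as high as 36% can be calculated for SEP2,** but that figure belongs to a 13-man arm, the size of the placebo group, not to 16,000 µg.
- **The equal-rise result is not about chi-square.** It applies to any within-arm test, including the IIEF paired t-test. That is right, so it supports ranking the analyses rather than faulting this test in particular.
- **Departure from the protocol's paired t or signed rank tests is permitted.** Protocol 10.3 says the methods will be updated. It may also be sensible: on percentages at Week 24 the paired t-test rejects in 10–22% under the null for SEP3.
- **The two baseline statements need not conflict.** SEP-specific text normally governs over a general rule, and a diary completed before dosing at Visit 2 naturally covers Visit 1 to Visit 2. What stands is an undated window and a synopsis that does not match the schedules.
- **The 16% without a baseline is a low-end case.** It assumes the minimum attempt rate and exactly 14 days. Visit 2 waits for laboratory results and drug shipment, so the gap may be longer.
- **Table shells and output lists not available here may settle the form of the test.** They may, but the choice of decisive analysis belongs in the SAP text.

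**Conclusion.** The point holds in two parts. First, the SAP names no decisive SEP analysis, and its within-arm test cannot address 16,000 µg versus placebo. With an assumed equal 20-point rise and no drug effect, that test is significant in the 16,000 µg arm in about 21–38% of trials, against about 5–6% for the ANCOVA already planned. Second, the form and unit of the chi-square are unstated. This matters less: the Pearson reading errs on the conservative side, and the choice between Pearson and McNemar changes the verdict in roughly 8–24% of trials in the 16,000 µg arm under an assumed 30-point rise.

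The baseline issue is a smaller one of definition: an undated period, no rule for men without a pre-dose attempt, and a mismatch between the synopsis and the schedules.

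The documents do not support saying that the plan specifies a wrong test or inflates error by design. All the sizes rest on assumed response rates and within-man correlations. That the within-arm test does not address the between-arm objective rests on none of them. The change should be made, but the planned SEP analyses remain usable once ranked.

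**What to change.** State in SAP Section 9.3:

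- For SEP2 and SEP3 each, the decisive analysis is the between-arm ANCOVA, 16,000 µg versus placebo, of the change in each man's percentage of yes, adjusted for baseline percentage. Give its post-baseline time frame (a visit or the whole period) and its alpha.
- The repeated measures logistic model, with participant as the cluster, and any within-arm test are supportive.
- If a within-arm test is kept, it is McNemar, one-sided, on one stated response per man.
- The SEP baseline is the percentage over the pre-dose Visit 1 to Visit 2 diary. It overrides the general rule in SAP Section 6. State how men with no pre-dose attempt are kept in the ANCOVA.

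Reconcile the protocol synopsis with Protocol Sections 6.2 and 7.1, Appendix B and the SAP schedule on when SEP collection starts.

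The cost is SAP wording and a correction to the collection schedule; the ANCOVA and the logistic model are already planned. There are two downsides. About two pre-dose attempts per man gives a coarse baseline, mostly 0, 50 or 100%. McNemar is very conservative for SEP3, with size at most 0.6% at a 5% rate. The change does not settle how SEP2, SEP3 and the erectile function domain are to be judged jointly.

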**ION04ED****9.4. Safety and/or further analysis**

The below parameters will be analyzed against the safety population as part of the safety analysis

- Adverse events
- Serious Adverse Events
- Clinical laboratory tests
- Electrocardiogram
- Physical examinations and Vital signs
- Pharmacokinetics Evaluations (Assays for hslo Maxi-K)

 **Adverse Events**

All the adverse events will be coded using the MedDRA Version 19.1. All the information collected in the AE form in the CRF and the preferred term, and system organ class corresponding to each reported term will be presented as a listing. In addition to this SAEs will be presented as a separate listing.

An overall summary table for the adverse events will be presented. All TEAEs recorded during the study will be further summarized in detail. The incidence of adverse events will be summarized by system organ class and preferred term within system organ class overall and by severity, relationship, outcome, action taken separately and DLT.

Summary tables corresponding to the AEs will contain the incidence of events and the number and percentage of subjects experiencing an adverse event. The percentages will be calculated with respect to the total number of subjects in the safety population. While counting the number of subjects, a subject with more than one adverse event with the same preferred term will be counted only once using the incidence with highest severity (severity, action taken and DLT tables), or strongest relationship to study treatment and most severe outcome for the respective tables. The descending order of the above characteristics will be considered as below

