5.2.1 Dose Limiting Toxicity

A DLT is defined as the occurrence within the first 4 weeks following a single administration of *hMaxi-K* of an unacceptable toxicity, as described below. Adverse events for cardiovascular, blood chemistry, complete blood count, or urine categories of adverse events will be graded according to the criteria provided in [Appendix A](#).

No acute toxicity was seen in the preclinical studies with administered doses up to 1000 μg (approximately 1500 $\mu\text{g}/\text{kg}$) or in men and women given doses up to 16000 μg . Potential toxicities would be those that could occur due to enhanced efflux of K^+ with resultant decreased intracellular Ca^{++} concentration thus altering smooth muscle function in diverse organ systems.

The following criteria will be used to define:

DLT:

- 1) Any adverse events of Grade 2 or higher in the cardiovascular category of adverse event criteria listed in [Appendix A](#);
- 2) Any adverse events of Grade 2 or higher in the blood chemistry, complete blood count, or urine categories of adverse event criteria listed in [Appendix A](#).

- 3) Penile pain and/or erection that persists for more than four hours after gene transfer;
- 4) Change in random hormone levels greater than 2 times the upper or lower limits of normal at any time post dosing..

Stopping Rule

If within 4 weeks following the single administration of *h*Maxi-K, if any participant experiences a grade 3 or higher dose limiting toxicity, no additional participants will be accrued and no further doses of *h*Maxi-K (or placebo) will be administered. Clinical data regarding the event will be collected, reviewed, and discussed with the Ethics Committee (EC) and Kuwait Ministry of Health (MOH). After review of these data with EC and MOH the clinical study may resume only with concurrence of EC and MOH.

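### The SAP chooses the record for the DLT subject count by severity, so the number of men with a DLT can come out too low

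*SAP*

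**What the plan says.** SAP 9.4 (Adverse Events) summarises treatment-emergent events by system organ class and preferred term, and then "by severity, relationship, outcome, action taken separately and DLT". Each table carries two kinds of count: "Summary tables corresponding to the AEs will contain the incidence of events and the number and percentage of subjects experiencing an adverse event". A once-only rule governs the second kind. Its scope is set by the opening words, "While counting the number of subjects, a subject with more than one adverse event with the same preferred term", and its effect is that such a man "will be counted only once using the incidence with highest severity (severity, action taken and DLT tables". Relationship and outcome are each ranked on a scale of their own. DLT status has no ranking and borrows the severity scale, which has three levels (Severe, Moderate, Mild).

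The events fed into these tables are not limited to the DLT window. SAP section 6 states: "All adverse events with start date on or after the date of treatment will be considered as TEAEs". Follow-up is about 6 months after the single injection (SAP section 3).

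Protocol 5.2.1 defines the DLT by time and by content: "A DLT is defined as the occurrence within the first 4 weeks following a single administration". Criterion 1 is "Any adverse events of Grade 2 or higher in the cardiovascular category of adverse event criteria listed in" the grading table (Appendix A), and criterion 2 sets the same Grade 2 threshold for blood chemistry, blood count and urine. Criterion 3 concerns penile pain or erection lasting more than four hours after gene transfer. Criterion 4 is "Change in random hormone levels greater than 2 times the upper or lower limits of normal at any time post dosing", which carries no 4-week limit.

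**The concern.** Picking one record per man by severity suits a severity table, because the record chosen shows the attribute being tabulated. In a DLT table the attribute is whether the man had a DLT, and severity is a poor guide to it. A Grade 2 cardiovascular event in week 2 is a DLT. A Grade 3 event of the same term in week 10 falls outside the window. The rule keeps the second record and the man takes its DLT status.

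What is at stake is the per-arm number and percentage of men with a DLT. Safety is the protocol's primary objective (section 2.0), and the dose arms are planned at 11 men each, so one misclassified man shifts the reported percentage visibly. The subject percentage would also disagree with the event count in the same table.

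**Working it through.** The plan states no figure on this point, so there is nothing to reproduce. The check applies the SAP rule to a constructed case and then sizes the effect of one man.

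**Inputs**
- Selection rule, subject counts only: SAP 9.4, Adverse Events.
- Period of events summarised: on or after treatment, with no 4-week cut (SAP section 6).
- DLT window of 4 weeks and Grade 2 threshold: protocol 5.2.1.
- Grade labels: Grade 2 is moderate and Grade 3 is severe (protocol Appendix A).
- Planned arm sizes: 11, 11 and 13 (SAP section 3), with the two doses combined as a cohort of 22 (SAP 9.2). All are assumed treated, so that they form the safety-population denominators.

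**Step 1. Constructed case: one man, one cardiovascular preferred term**

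| Record | Week | Severity | Within 4 weeks | DLT under 5.2.1 |
|---|---|---|---|---|
| A | 2 | Moderate (Grade 2) | yes | yes |
| B | 10 | Severe (Grade 3) | no | no |

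- SAP rule: the more severe record is B, so the man is DLT = No.
- Any-occurrence rule: A qualifies, so the man is DLT = Yes.
- DLT event count: 1 under both rules.

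**Step 2. Direction of the error.** Under the SAP rule a man is DLT = Yes only if his selected record is a DLT. Every such man did have a DLT. The men counted by the SAP rule are therefore a subset of the men with any DLT, and the count can be too low but never too high.

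**Step 3. When a man is lost**
- Graded categories (criteria 1 and 2): a worse episode inside the 4 weeks is itself at least Grade 2 and so is itself a DLT. Loss needs a strictly worse episode of the same term after week 4.
- Criterion 3 turns on duration, and penile pain is not in Appendix A, so it is graded on symptom intensity (protocol 9.4). A later, more intense episode that does not meet criterion 3 would displace the qualifying one, even inside 4 weeks.
- Ties: with a Grade 2 event in week 2 and another in week 10, the rule does not say which is kept. The protocol uses four grades and the SAP three levels. If Grades 3 and 4 both map to Severe, which the SAP does not say, ties become more likely.
- Criterion 4: post-dose hormones are measured at week 1 and week 24 only (protocol 6.6). A week 24 change is a DLT by the wording of criterion 4 and is not one by the 4-week definition.

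**Step 4. Size of one man lost, if he is the only DLT case** (exact Clopper-Pearson 95% intervals, added for scale)

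| Group | SAP rule | Any-occurrence rule | Difference |
|---|---|---|---|
| One dose arm | 0/11 = 0% (0 to 28.5%) | 1/11 = 9.1% (0.2 to 41.3%) | 9.1 points |
| Doses combined | 0/22 = 0% (0 to 15.4%) | 1/22 = 4.5% (0.1 to 22.8%) | 4.5 points |

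One man on placebo is 1/13 = 7.7 percentage points.

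**The case against.** Four points can be made for the plan as it stands.

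*The data are not lost.* The once-only rule applies to counts of subjects. Event incidence in the same table and the listing of the adverse event form both keep the qualifying event. This stands. A reader might infer that the DLT drops out of the report altogether, and SAP 9.4 does not support that.

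*The layout is unknown.* SAP 9.1 refers to shells and programming notes that are not in the documents. A table restricted to DLT events would lose nobody. This stands as a condition. It does not dispose of the point, because choosing a record by severity affects a DLT count only if all treatment-emergent events are split by DLT status, and the SAP names the DLT table in that rule.

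*DLT is not a named endpoint.* A reader might take the DLT rate for the trial's main toxicity measure. The documents do not say so: the safety endpoints are adverse events, laboratory tests, ECG and physical examinations. In the protocol, the DLT criteria serve the stopping rule (5.2.1) and 24-hour reporting to the sponsor (9.5). Both act on individual events and are untouched. The design is single-dose and parallel, so no escalation step uses the tabulated rate. All of this stands and limits the point to reporting.

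*The sequence may be rare.* It needs a DLT and then a worse non-DLT episode of the same term in the same man. Protocol 5.2 reports one possibly related event among 20 men treated earlier. That figure does not bound DLT frequency, since criteria 1 and 2 make no mention of relatedness. Equally, no percentage of recurrences lost can be given, because the documents supply neither a grade distribution nor the timing of recurrences.

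A reader might also carry the criticism over to the action-taken table. The SAP gives no order for actions, and reporting the action attached to the worst episode is a coherent choice, so the same fault is not shown there.

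**Conclusion.** The point holds for the number and percentage of men with a DLT. The selection key in SAP 9.4 is the wrong one for a DLT table, the error runs only downward, and ties have no stated resolution. Each man affected is worth 9.1 percentage points of an 11-man arm.

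The conclusion rests on three assumptions: the table splits treatment-emergent events by DLT status, the planned arm sizes are reached, and at least one man has a qualifying DLT together with a more severe non-DLT episode of the same term. How often the last occurs cannot be estimated from the documents. The correction is worth making before unblinding because it is nearly free and removes a one-directional error.

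**What to change.** In SAP 9.4:
- Remove the DLT table from the list governed by highest severity.
- State that a man is DLT = Yes for a preferred term if any of his occurrences of that term meets protocol 5.2.1, and DLT = Yes overall if any occurrence of any term does. This also settles ties.
- Add a row for men with at least one DLT, by arm and for the doses combined.

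In protocol 5.2.1, reconcile the 4-week definition with the open-ended hormone criterion so that every event has a determinate DLT status. Which reading applies is for the sponsor to decide, and the SAP should then follow it.

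The cost is a few sentences and a small programming change. No new data, visits or sample size are needed.

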9.4 Severity of Adverse Event

Adverse events included in the toxicity table ([Appendix A](#)) will be graded according to the definitions provided. For adverse events not listed in the toxicity table, assignment of grade based on intensity of symptoms, degree of limitation of usual daily activities, or level of abnormality of objective clinical signs or laboratory parameters will be according to severity using the following criteria:

- Grade 1: transient or minimal symptoms; not interfering in function or ability to perform activity of daily living or require a medication change. No medical intervention required.
- Grade 2: symptoms interfering in function but not with activities of daily living. Minimal or no medical intervention required.
- Grade 3: incapacitating symptoms that interfere with function and activities of daily

living; required bed rest and/or resulted in loss of work or cancellation of social activities. Medical intervention required. Hospitalization possible.

- Grade 4: Considered potentially life threatening (see definition under section 9.2)

A serious adverse event (SAE) requires medical intervention to prevent permanent impairment or death, permanently disability: (bed-ridden or disabling AE), required significant medical intervention/therapy, hospitalization or hospice care or in the judgment of the investigator was a medically significant event. Serious adverse events may be mild, moderate or severe in intensity (e.g., mild stroke).

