**• Severity /Toxicity grade**

- Severe
- Moderate
- Mild

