**• Outcome**

- Condition Deteriorated
- Still Present
- Improving
- Recovered with Sequela
- Recovered
- Other

Serious AE are defined as the following:

- Medically significant events (e.g., intensive treatment in ER or at home for allergic bronchospasm)

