**ION04ED**

- life threatening
- requiring hospitalization
- resulting in death
- resulting in a disability
- resulting in a congenital abnormality

Similar tables will be presented for serious adverse events. Deaths will be reported as AE term in the CRF. Deaths and other serious adverse events will be listed.

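### The ranking lists in SAP 9.4 leave out the protocol's Grade 4 and any fatal outcome and place Other below Recovered, so the adverse event summary tables can misclassify the gravest events

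*SAP*

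**What the plan says.** SAP section 9.4 (Adverse Events) sets a worst-case rule for subject counts: "a subject with more than one adverse event with the same preferred term will be counted only once using the incidence with highest severity" for the severity, action-taken and DLT tables, or "strongest relationship to study treatment and most severe outcome for the respective tables". It then states that "The descending order of the above characteristics will be considered as below", so the lists that follow are rankings from worst to least.

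- Under "Severity /Toxicity grade" the order is Severe, Moderate, Mild.
- Under Outcome the order starts at "Condition Deteriorated" and continues Still Present, Improving, Recovered with Sequela, Recovered, Other.

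The protocol uses four grades. Its section 9.4, for events outside the toxicity table, ends with "Grade 4: Considered potentially life threatening (see definition under section 9.2"). Appendix A has four columns, in which Severe is Grade 3 and Grade 4 stands apart.

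The SAP also says "Deaths will be reported as AE term in the CRF", lists deaths and other serious events, and promises tables of the same kind for serious adverse events.

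**The concern.** A worst-case rule works only if its ranking contains the worst case and puts it first. The severity list is headed as a toxicity grade but omits the protocol's top grade. The outcome list has no level for death, which both documents name as a criterion for a serious event. It also ranks an undefined category as milder than full recovery.

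Safety is the protocol's primary objective (section 2.0), and the SAP puts it in both its primary and its secondary objective (section 4). This is a single-dose gene-transfer trial with arms of 11, 11 and 13. The by-severity and by-outcome tables should be able to show a life-threatening or fatal event as such.

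**Working it through.** The plan states no figure to reproduce. The check sets the lists side by side and applies the SAP's rule to them.

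**Step 1: severity.** Inputs are the four grades of Appendix A and the three SAP levels.

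| Protocol grade | Appendix A label | Level in SAP 9.4 |
|---|---|---|
| 1 | Mild | Mild |
| 2 | Moderate | Moderate |
| 3 | Severe | Severe |
| 4 | Potentially life-threatening | none |

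Three of four grades have a level. Grade 4 must be folded into Severe or left without a row, and the SAP gives no mapping. This applies to every Grade 4 event, whether it occurs once or recurs.

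**Step 2: tables that borrow the severity order.** Highest severity also selects the record for the action-taken and DLT tables. Suppose a man has a Grade 3 and a Grade 4 episode of one preferred term and both become Severe. They tie, and no tie-break is given. The two records need not agree on action taken or on DLT status, because the protocol ties its DLT definition to the first 4 weeks (section 5.2.1).

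**Step 3: outcome.** None of the six levels is fatal. Pairing Other with each of the five remaining levels, the rule picks the remaining level every time:

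| Two episodes of one term | Counted as |
|---|---|
| Condition Deteriorated, Other | Condition Deteriorated |
| Still Present, Other | Still Present |
| Improving, Other | Improving |
| Recovered with Sequela, Other | Recovered with Sequela |
| Recovered, Other | Recovered |

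The last row is the fault: an outcome of unknown gravity gives way to full recovery.

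**Step 4: do the serious-event tables close the gap?** Not fully. A Grade 4 laboratory value under Appendix A, such as BUN above 50 mg/dL, need not be a serious event. Protocol section 9.2 reserves life-threatening for a participant at risk of death at that moment. The SAP's laboratory tables do not help, because they classify results only as high, low or normal. The serious-event tables are described as similar with no other ranking, so they appear to inherit the same lists.

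**Step 5: scale.** One man is 1/11 = 9.1% of an active arm or 1/13 = 7.7% of the placebo arm. This shows how much one misplaced count moves a table. It does not estimate how often that will happen.

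**The case against.** The strongest reply is that nothing is lost from reporting. Death is entered as an adverse event term and so has its own row. Deaths and serious events are listed, the termination listing carries the date of death, and every item on the adverse event form is listed. With about 35 men, those listings can be read in full. All of this stands, and it limits the point to the summary tables.

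The worst-case rule also governs subject counts only; event counts are not collapsed. So the rank of Other changes a figure only when one man has the same preferred term more than once with different outcomes. That stands too, but it does not help with Grade 4, which has no row in either kind of count.

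Protocol section 9.4 itself describes serious events in three intensity words, and the case report form may do the same. Even so, the protocol's grading scale has four levels, and the SAP list claims to be a toxicity grade.

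A reader might infer three stronger things that the documents do not support:

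- **That the stopping rule is weakened.** Its threshold is Grade 3 and above (protocol section 5.2.1), so merging Grades 3 and 4 cannot change whether it is met. It also acts on individual events during the trial, not on these tables.
- **That a fatal episode would be tabulated as recovered.** This assumes that death is coded Other, which neither document says. Condition Deteriorated, the top level, is equally available. Because death is its own term, a recovered episode of that same term is not to be expected.
- **That "Recovered with Sequela" is wrongly placed below Improving.** Ranking unresolved states above resolved ones is a coherent choice, and no text requires another.

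**Conclusion.** The point holds as a table-specification fault worth correcting. The SAP's severity ranking does not match the protocol's own scale: one of four grades has no level, with effects in the severity, action-taken and DLT tables. The outcome ranking cannot show a death as fatal, and it treats an undefined outcome as the mildest. No test, power figure or stopping decision is affected.

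The conclusion rests on the SAP text being followed as written. The index of tables in SAP section 10 and the table shells are not available here, so extra categories in the shells cannot be ruled out. How the case report form records grade and fatal outcome is also unknown.

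**What to change.** In SAP section 9.4 and the table shells:

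1. Replace the severity order with the protocol's Grades 4, 3, 2, 1, and use it for the severity, action-taken and DLT tables.
2. Add Fatal at the top of the outcome order.
3. Take Other out of the ranking and report Other/unknown as its own category. State how a man with both a ranked and an Other outcome for one term is counted, for example in both rows with a footnote.
4. State that the serious-event tables use the same corrected lists.

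The cost is a few lines of text and some extra table rows. If the case report form already holds the protocol grade, no new data are needed. If it holds only three levels, the SAP should say how Grade 4 is derived, for instance from the Appendix A limits for laboratory parameters. The change belongs in the final SAP, which protocol section 10.3 requires before the treatment code is broken.
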